The Use of Tranexamic Acid to Reduce Blood Loss in Acetabular Surgery

Primary Investigator:
[name]

Co-Investigator:
[name]
[name]
[name]
[name]
[name]
[name]
[name]

Protocol Version:3
Protocol Date: 4/15/2013

Background and Significance:

Orthopaedic surgery carries with it a significant risk for blood loss. Historically, this blood loss has been managed with allogenic blood transfusion when necessary. However, in recent years there has been a strong push to reduce the use of allogenic blood.[6, 9,24,34] Even in developed countries, the demand for allogenic blood frequently exceeds the supply, and although multiple safety measures are in place to prevent “wrong blood” transfusions, the incidence of clerical errors is still unacceptably high, ranging from 1/15,000-1/20,000.[23] Allogenic blood carries with it a risk for HIV and Hepatis C, as well as multiple adverse reactions.[23] Furthermore, allogenic blood transfusion is known to have significant immunomodulatory effects, and the results of three extensive studies, involving more than 22,000 orthopaedic patients, showed that allogenic blood transfusion significantly increases the risk of postoperative infection.[5, 7, 29] Thus, significant effort has been expended toward reducing allogenic blood transfusion in orthopaedic surgery.

Multiple anti-fibrinolytic agents have been used for this purpose, including tranexamic acid (TXA), aprotinin, and epsilon-aminocaproic acid (EACA). Of these three, TXA has been the most widely used in recent orthopaedic studies.[21] Reasons for this include the fact that aprotinin has a higher mortality rate than either TXA or EACA.[12] Furthermore, TXA is the cheapest of the three and has excellent penetration of the major joints.[35] Thus, we feel that TXA is the most appropriate anti-fibrinolytic for further study.

Specific Research Questions:

1. Do patients undergoing acetabular ORIF who receive tranexamic acid have a reduced risk of allogenic blood transfusion as compared to patients who receive placebo?
2. Do patients undergoing acetabular ORIF who receive tranexamic acid have reduced peri-operative blood loss as compared to patients who receive placebo?
3. Do patients undergoing acetabular ORIF who receive tranexamic acid have a higher risk for thromboembolic events than patients who receive placebo?
4. Do patients undergoing acetabular ORIF who receive tranexamic acid have a reduced risk of wound complications (prolonged wound drainage, return to the OR within 30 days, infection)?
5. Is the use of tranexamic acid cost effective relative to the use of allogenic blood transfusion as a blood loss management strategy in acetabular ORIF?

1. *Do patients undergoing acetabular ORIF who receive tranexamic acid have a reduced risk of allogenic blood transfusion as compared to patients who receive placebo?*

The ability of TXA to reduce the use of allogenic blood transfusion relative to placebo is unclear. The largest ever study on the use of TXA was conducted in general trauma patients, and included 10,096 patients randomized to receive TXA, and 10,115 randomized to receive placebo with an equivalent dose of normal saline.[33] This study showed no significant difference in the incidence of blood transfusion between groups (relative risk of transfusion with TXA of 0.98, 95% CI 0.96-1.01).

Multiple studies have attempted to answer this question specifically in joint arthroplasty patients and the results have been mixed. Several studies in total joint arthroplasty found no benefit of TXA relative to a saline placebo.[4,13,14,27] In contrast, at least 5 other prospective studies of joint arthroplasty patients have shown at least a mild reduction in the risk of transfusion with use of TXA in total joint arthroplasty.[2,8,11,18,26] A meta-analysis of these studies in total joint patients showed a transfusion benefit of TXA relative to placebo, with a risk difference of -.20 (-0.20, 95% CI -0.29 to -0.11).[35] These results were consistent with two other meta-analyses, which included orthopaedic patients from all of the sub-specialties, and estimated that use of TXA reduced the incidence of blood transfusion by up to 50%.[21,39] However, the authors noted that none of the prior studies in orthopaedics have ever included more than 150 patients, and called for a large prospective randomized trial in order to clarify the differences in reported literature.[14,21,35,39]

In this study, we plan to prospectively record the overall incidence of allogenic blood transfusions. In addition, we will record the total number and volume of allogenic blood products required by each patient. We do not plan to use erythropoietin in any of our patients. This study will not have a specific “transfusion trigger.” Previous studies have advocated for blood transfusions to be based on an overall assessment of the patient’s physiologic status, and not an arbitrary “transfusion trigger.”[6,9,34] We agree that you should treat the patient and not a number, and thus the decision to transfuse will be left up to the individual treating surgeon. While the decision to transfuse will thus be subjective, and could possibly differ between surgeons, the fact that our study is double blinded and randomized should account for this potential source of bias. Overall, we hypothesize that our study will demonstrate a reduction in the incidence of allogenic blood transfusion in patients that receive TXA, regardless of dosing, as compared to patients who receive a saline placebo.

2. *Do patients undergoing acetabular ORIF who receive tranexamic acid have reduced perioperative blood loss as compared to patients who receive placebo?*

There have been at least three meta-analyses of prospective randomized trials in orthopaedics which attempted to answer this question, and each meta-analysis has consistently shown reduced perioperative blood loss with the use of TXA relative to placebo.[21,35,39] Specifically in total joint arthroplasty, patients who received TXA had a mean of 289 ml less peri-operative blood loss, as compared to patients who

received a saline placebo.[35] However, a separate meta-analysis isolated to total hip arthroplasty patients showed no benefit for TXA in terms of reduced blood loss.[14] Furthermore, the magnitude of reduction in peri-operative blood loss varied significantly between studies, and as reported above, the correlation between this result and with decreased risk of transfusion is not clear. Two studies of this outcome in hip fracture patients found trends toward decreased transfusion risk.[32,40]

In this study, we plan to report intra-operative blood loss based on the estimated blood loss (EBL) dictated into the procedure note at the time of surgery. The EBL is an estimate based on the amount of blood remaining in sponges and drapes, as well as in suction containers at the end of the case. Although this measurement has a subjective component, the fact that our study will be double blinded, and that patients will be randomized to the different treatment groups should reduce potential bias.

In order to objectively quantify peri-operative blood loss, we will report total peri-operative blood loss based on the formula derived by Gross,[16] where peri-operative blood loss = estimated blood volume \times (haematocrit reduction/mean haematocrit), and blood volume is estimated with the formula: Blood volume (BV) (ml) = 70 \times weight (kg).[25] Since these calculations will be based on objective laboratory values, this should further help to control for any potential bias introduced by the subjective nature of the EBL measurement. Overall, we hypothesize that TXA will reduce peri-operative blood loss relative to placebo.

3. *Do patients undergoing acetabular ORIF who receive tranexamic acid have a higher risk for thromboembolic events than patients who receive placebo?*

This is a key question that has not been answered by prior studies of TXA in orthopaedics. TXA is a lysine analogue that functions by inhibiting the conversion of plasminogen to its active form plasmin. Since plasmin is responsible for the breakdown of fibrin in clots, TXA's mechanism is presumably one of decreased clot breakdown. Theoretically, TXA could thus place the patient at increased risk for thromboembolic events. However, previous studies have shown that TXA exerts its effects mostly in the wound bed,[3] and that it has no effect on fibrinolytic activity in the wall of the veins.[1] Therefore, the effect of TXA on thromboembolic events should be minimal.

This presumption is borne out by the fact that none of the previous meta-analyses on this topic in orthopaedics has ever demonstrated a significantly increased risk of thromboembolism following the use of TXA.[14,21,35,39] However, only two studies have been performed in orthopaedic trauma and these studied hip fracture patients. [32,40] Additionally, no prospective clinical trial of TXA in orthopaedics has ever included more than 150 patients, and the meta-analyses were markedly underpowered to detect clinically significant differences in the incidence of DVT.

Patients will be treated in standard fashion with mechanical and anticoagulant prophylaxis against VTE as appropriate based on the clinical scenario. Symptomatic venous thromboembolism will be diagnosed by history, exam, and standard tests. We will not screen for asymptomatic DVT. The American Academy of Orthopaedic Surgeons guidelines on DVT prophylaxis recommend against screening asymptomatic patients

with Doppler ultrasound and there are significant questions regarding the correlation between DVT and more significant outcomes such as PE. Although our study will not be specifically powered for other thromboembolic outcomes, we will also prospectively record the incidence symptomatic thromboembolic events such as pulmonary embolism, stroke, and myocardial infarction. We hypothesize that there will be no increased risk of thromboembolic events in patients receiving TXA, regardless of dosing, as compared to patients receiving placebo.

4. *Do patients undergoing acetabular ORIF who receive tranexamic acid have a reduced risk of wound complications (prolonged wound drainage, return to the OR within 30 days, infection)?*

This is an important question as decreasing blood loss may reduce transfusion risk as well as risk of drainage and hematoma formation, with the potential to decrease risk of infection. This has not yet been shown to be true in orthopaedics, let alone orthopaedic trauma surgery. The incidence of infection with acetabular ORIF has been reported to be 2 to 5% in general populations and up to 15% in morbidly obese patients and showing a decreased infection rate with tranexamic acid would be a very important finding. Infection and associated outcomes including wound drainage and return to the OR for drainage and hematoma evacuation can be recorded to study the affects of tranexamic acid on wound healing.

5. *Is the use of tranexamic acid cost effective relative to the use of allogenic blood transfusion as a blood loss management strategy in acetabular ORIF?*

A few small previous studies have shown TXA to be cost effective relative to a placebo in orthopaedic patients.[20,26,28] However, the majority of trials have not reported on cost-effectiveness, and meta-analyses on this topic have not been able to draw definitive conclusions on this issue.[8,13,15,19,21,27,35,39] Neither of the two studies in orthopaedic trauma, specifically hip fracture patients, reported on this. [32,40] In this study, we will calculate the cost of tranexamic acid administration in each treatment group, and compare this to the total cost of allogenic blood transfusion in each treatment group. Since TXA is an inexpensive drug, we hypothesize that TXA will be a cost effective blood loss management strategy with acetabular ORIF.

We plan to enroll 50 patients (N=25 treatment, N=25 controls) in a pilot study to test procedures and collect preliminary data. While this pilot study will likely not have sufficient power to definitively address the specific aims and hypotheses, the preliminary data collected will provide information to plan future work.

Study Design:

Eligibility:

Inclusion Criteria: All patients aged 18 or above undergoing acetabular ORIF.

Exclusion Criteria:

- All patients aged below 18 undergoing acetabulum surgery
- Patients with color-blindness (color vision changes used to assess toxicity)
- Patients with subarachnoid hemorrhage.
- Patients with active intravascular coagulation.
- Patients with a previous history of venous thromboembolism or with a history of hypercoagulable conditions (i.e. Factor V Leiden, antiphospholipid antibody).
- Prisoners
- Pregnant women

Patient Consent:

Orthopaedic surgery attendings and residents will identify potential study candidates during the initial consultation based on the presence of an acetabular fracture. If the patient meets the inclusion and exclusion criteria (noted above), a member of the treatment team will discuss the study with eligible patients. If the patient expresses interest in the study, the physician will notify the research staff. Orthopaedic Clinical Research staff will describe study procedures in detail and go through the informed consent process to enroll the patient in the study. The number of eligible patients, and the eventual number enrolled will be specifically reported.

Dosing:

Multiple different treatment regimens with TXA have been proposed, with doses ranging from as little as 10mg/kg in a single dose, up to a total of 2g given as an infusion throughout the peri-operative period.[21,33,35] No prospective study has ever directly compared the efficacy of different dosing regimens. Two previous meta-analyses showed a trend towards decreased peri-operative blood loss with increasing doses of TXA in orthopaedic patients.[35,39] However, both of these studies, in spite of being meta-analyses, were underpowered to demonstrate a significant treatment effect of the higher dose regimens. Furthermore, neither meta-analysis reported on differences in the incidence of complications with higher dose regimens. Thus, the safety and efficacy of different dosing regimens of TXA remains poorly defined. Since TXA is potentially a prothrombotic agent, a clear understanding of the thrombotic potential of a high dose regimen would be critical prior to making definitive treatment recommendations. In this study, we plan to administer a 10mg/kg dose within 30 minutes of surgery followed by a 10mg/kg infusion over a 4hr period to the treatment group (for patients weighting over 100kg, a weight of 100kg will be used for the dose calculation). The control group will receive equal volumes of and rates of normal saline.

Stratification:

Stratification by known prognostic factors prior to randomization is a commonly employed technique to optimize balance of known prognostic factors between study groups.[17] Preoperative hemoglobin values have been shown to be the strongest predictor of transfusion following major orthopaedic surgery.[31] Enrolled patients will be stratified based on their preoperative hemoglobin value prior to randomization. The three groups they will be stratified into will be based on previous researching categorizing the risk of transfusion by preoperative hemoglobin into three groups (< 13 g/dL, 13 to 15 g/dL, and > 15g/dL).[31]

Randomization:

Study participants will be stratified as described above and then block randomized and assigned by sequentially numbered sealed opaque envelopes to one of the two treatment groups based on computerized selection.

Blinding:

The study coordinator completing the randomization and the statisticians analyzing the data will not be involved in the treatment of the patient. The Investigational Pharmacy will provide treatment packs that are identical in appearance and differ only by their random number, it will not be possible for either the treating physician, or the patient to know the treatment regimen received.

Unblinding:

In general, it should not be necessary for unblinding to occur. If a contraindication to the treatment regimen develops after randomization (i.e. suspicion of allergic reaction to the treatment), the treating physician will contact the study coordinator immediately to explain the reasons behind the request for unblinding. A thromboembolic event will not be considered a reason for unblinding, as this is a primary outcome measure. However, the rate of thromboembolic events will be monitored and if this rate is noted to be higher than the baseline rate in patients undergoing acetabular ORIF, this will trigger a safety evaluation. Patients whose treatment is unblinded in this manner will be excluded from the final data analysis. The numbers of patients unblinded, and the reasons for the decisions will be specifically reported.

Patient Safety Monitoring

A data safety monitor will be appointed for this study. This person will otherwise be uninvolved in the planning or execution of this trial but will have the ability to unblind the collected data to analyze and determine if subjects experiencing an unacceptably high level of adverse events. There had not been adverse effects of tranexamic acid reported. For this reason, only adverse events outside of what would reasonably be expected for a typical post-operative trauma patient will be considered. These adverse events will be assessed by the treating physicians at every follow-up appointment (2 weeks, 6 weeks, 3 months, and 6 months), who will notify the data safety monitor within 24 hours. If deemed necessary, the data safety monitor will unblind the collected data and determine

if the study group is experiencing adverse events at a significantly higher rate or with greater severity than the control group. If the risk to patients is deemed unacceptably high by the data safety monitor, the study will be terminated and the results will be published.

Sample Size and Feasibility:

Pilot Study:

We plan to enroll 50 patients to test the study procedures and collect preliminary data. These patients will be randomized to 25 patients receiving the intervention and 25 receiving placebo. Results from the pilot study will be used to determine the need for expansion to a fully powered study and to aid in seeking funding for this further investigation.

Future Investigation:

We conducted a power analysis to determine the sample size necessary to demonstrate a treatment effect transfusion risk. Average perioperative blood loss with acetabular ORIF has been reported to be approximately 1300cc as reported in the literature by one of the study investigators. [22] The combined rate of intraoperative and postoperative allogeneic transfusion has been reported to be 58% in a study performed at the study institution (Carolinas Medical Center).[32] We plan to power our study to detect a 30% difference in intraoperative and postoperative allogeneic transfusion. Assuming an alpha value of 0.05 and a power of 0.8 this requires a study population of 212 patients.

Assuming a transfusion rate of 58% we would need 106 patients in each treatment group to detect a 30% decrease in transfusion rate with a power of 0.8 and an alpha of 0.05, for a total study population of 212 patients.

Given the incidence of infection with acetabular ORIF has been reported to be 2 to 5% in general populations and up to 15% in morbidly obese patients, our study will likely be underpowered to detect changes in this outcome. [22,36] Secondary outcome measures including wound drainage and return to the OR for drainage and hematoma evacuation will also be used to study affects on wound healing.

Data Collection:

The data points listed below will be prospectively collected for each patient. The randomization number of each patient will be included in this report, and our study coordinator will use this to divide the aggregate data into the three treatment groups. This aggregate data will then be given to our statisticians in order to complete the data analysis.

1. Patient Demographic Data (Age, BMI, Gender, Race, Type of Insurance).

2. Patient Medical Comorbidities, including Diabetes, HTN, CAD, Smoking History, Alcohol Use, Cardiac, Gastro-Intestinal, Genito-Urinary, Pulmonary, or Renal Disease.
3. Type of anesthesia used (Spinal or General).
4. Type of implant used in the surgery.
5. Operative Time.
6. Preoperative PT/INR and platelet count

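### The thromboembolic trigger compares one rate, apparently pooled over both arms, with an unstated baseline and no margin, so firing says little about TXA; the by-arm review that could settle the matter is discretionary and not linked to it.

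*Combined protocol and SAP*

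**What the plan says.** The Unblinding section treats thromboembolism as too important to unblind for: "A thromboembolic event will not be considered a reason for unblinding, as this is a primary outcome measure". Events are followed as a rate instead, and the condition for acting is "if this rate is noted to be higher than the baseline rate in patients undergoing acetabular ORIF". The stated consequence is an evaluation and not a stop: "this will trigger a safety evaluation". No baseline rate for thromboembolism appears anywhere in the document. The only complication rates given for this operation are for infection (2 to 5%, and up to 15% in morbidly obese patients). There is also no margin, minimum number of events, time window or look schedule.

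The next section, Patient Safety Monitoring, appoints a data safety monitor who "will have the ability to unblind the collected data to analyze". A comparison of the arms is provided for, but only where it is thought necessary. The question put to the monitor is then "if the study group is experiencing adverse events at a significantly higher rate or with greater severity than the control group". No test or threshold is given. The same section limits the adverse events considered to those that would be unusual after trauma surgery.

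The events are defined in Data Collection, item 12: symptomatic DVT, PE, MI and stroke. The discussion of research question 3 rules out screening for silent DVT. The exclusion criteria remove "Patients with a previous history of venous thromboembolism or with a history of hypercoagulable conditions".

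**The concern.** The safety question is whether TXA causes thromboembolism, and the trial has a concurrent placebo arm to answer it. The trigger, read naturally, does not use that arm.

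- **Dilution.** If the arms are pooled, half the patients are on placebo. A doubling on TXA raises the pooled rate only 1.5-fold: (1 + 2)/2.
- **No margin.** Any excess over the expected rate counts, so chance alone will often fire the rule.
- **Unstated reference.** A rate from unselected acetabular ORIF patients, or one that includes screened DVT, could differ from the trial's own placebo rate in either direction.

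What then matters is what follows a trigger. Nothing says that the evaluation must look at the arms. Ordinary DVT or PE after pelvic trauma may be judged expected and never reach the monitor. The protocol itself calls TXA potentially prothrombotic, so this is the adverse outcome for which the monitoring most needs to work.

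**Working it through.** The plan states no operating characteristics for the trigger, so there is no figure to reproduce. They were computed as follows.

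**Inputs.** From the plan: 25 patients per arm (Sample Size and Feasibility), and a trigger when the observed rate exceeds the baseline. Assumed: baseline *b* of 2%, 5% or 10%, equal to the true placebo rate unless stated; harm means that the TXA risk is doubled; the arms are pooled.

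**One look at 50 patients.** X = Bin(25, b) + Bin(25, b × RR). The rule fires if X > 50b. For b = 5%, 50b = 2.5, so 3 events are needed. With no harm, X is Bin(50, 0.05):

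P(X ≥ 3) = 1 − (0.0769 + 0.2025 + 0.2611) = 0.459.

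**Check after every patient.** The rule fires if events/patients > b at any point (400,000 simulated trials, 1:1 in pairs, each outcome known at once). At b = 2% the harmless case can be checked by hand. One event among the first 49 patients is enough (1/49 > 2%), and a first event at patient 50 is not, so P = 1 − 0.98^49 = 0.63.

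| Assumed baseline | Events needed at n = 50 | One look: harmless / doubled (ratio) | Every patient: harmless / doubled (ratio) |
|---|---|---|---|
| 2% | 2 | 0.26 / 0.45 (1.7) | 0.63 / 0.78 (1.2) |
| 5% | 3 | 0.46 / 0.74 (1.6) | 0.74 / 0.89 (1.2) |
| 10% | 6 | 0.38 / 0.78 (2.0) | 0.82 / 0.96 (1.2) |

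Five looks, one every 10 patients, fall between: 0.56 / 0.72, 0.64 / 0.84 and 0.56 / 0.87 (ratios 1.3 to 1.5).

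**What the ratios mean.** As an illustration, suppose the prior probability of a doubling is 20% (odds 0.25). A ratio of 1.6 moves it to 0.40/1.40 = 29%. A ratio of 1.2 moves it to 0.30/1.30 = 23%.

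**Wrong reference.** The reference is set at 5%.
- True placebo rate 2.5%, TXA risk doubled: fires in 0.29 of trials at one look and 0.61 if checked after every patient.
- True rate 10% in both arms, no harm: fires in 0.89 at one look.

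**Would a by-arm rule do better?** Take a rule that fires when TXA leads placebo by 3 or more events at any time:

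| Placebo rate | Harmless | Doubled |
|---|---|---|
| 2% | 0.01 | 0.06 |
| 5% | 0.06 | 0.28 |
| 10% | 0.17 | 0.59 |

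In the scenario with a true placebo rate of 2.5% it fires in only 0.09. A one-sided Fisher test at 0.05 with 25 per arm detects a doubling in 0.2%, 4.0% and 15.9% of trials at placebo rates of 2%, 5% and 10%. Comparing the arms makes a signal more specific and removes the external rate, but in 50 patients it loses much sensitivity.

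**The case against.** The best defence is that the plan has two stages: a sensitive blinded screen, followed by a review in which the monitor may unblind, compare the groups and end the study. A screen may fire often, because a false alarm costs one evaluation and not a stop. This is also a 50-patient pilot that the protocol expects to be underpowered. Much of this stands, and it is the reason to keep the screen.

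Three stronger readings are tempting, and the documents do not support them.

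- **That the trigger fires almost as often without harm as with a doubled risk.** This is roughly so only if the rate is checked after every patient, and the plan gives no schedule. At one look and a 5% baseline the figures are 0.46 and 0.74.
- **That the plan never compares the arms.** Patient Safety Monitoring does provide for it.
- **That a mismatched reference will hide real harm.** No reference is named, so a mismatch is a risk and not a fact. The 0.29 figure also belongs to a single look, and it should not be set beside false-trigger rates from continuous checking.

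Pooling is likewise an inference. It rests on the wording of a single rate, an external comparator, and the refusal to unblind for these events.

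The two-stage defence does not close the gap, because the text never joins the stages. The by-arm review happens only if thought necessary, and the filter on expected events may keep the relevant cases out of it.

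**Conclusion.** The point holds as a gap in specification and linkage. As written, the trigger cannot be applied without a baseline figure. On the pooled reading, it fires in roughly a quarter to a half of harmless trials at one look and in about two thirds to four fifths if checked after every patient. A doubling makes it only 1.2 to 2.0 times as likely to fire. A trigger should therefore open a comparison of the arms and should not itself count as evidence about TXA.

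These sizes rest on assumed baselines of 2% to 10%, a doubling as the harm of interest, pooled arms and immediate outcomes. The range across baselines and schedules is wide, which is itself a reason to state both.

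A reader might infer that the sentence should be replaced by a fixed excess of 3 events. That does not follow: such a rule would miss about 72% of doublings at a 5% placebo rate and about 94% at 2%. Choosing between more false alarms and more missed harm is a trade-off for the sponsor and the monitor.

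**What to change.** Keep the trigger as a screen that leads to an evaluation, and amend the two sections so that they connect:

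1. Say whether the monitored rate is pooled or by arm.
2. State the reference rate, its source, its time window and its population, which should match the trial: symptomatic events in patients without prior VTE or a hypercoagulable condition. State the look schedule.
3. Require that every symptomatic DVT, PE, MI and stroke goes to the data safety monitor, whether or not it would be expected after trauma surgery.
4. Require the monitor to tabulate these events by arm at each event, or each time the trigger fires, and to base the evaluation on TXA versus placebo.
5. If a count threshold is wanted, let the sponsor and monitor set it, with its false-trigger and detection probabilities shown over a range of placebo rates.
6. Say that the monitor's tabulation is not an unblinding that removes a patient from the final analysis, since the Unblinding section excludes unblinded patients.

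The cost is protocol wording and a short table for the monitor to maintain. The one downside is that the monitor routinely sees the allocation of event cases. The plan already permits this, and treating physicians and patients stay blinded.

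### Patients unblinded after randomisation for a suspected treatment reaction are dropped from the final analysis, and nothing restores them to their randomised arm

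*Combined protocol and SAP*

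**What the plan says.** The Unblinding section gives the trigger as "If a contraindication to the treatment regimen develops after randomization (i.e. suspicion of allergic reaction to the treatment"). The treating physician then asks the study coordinator for unblinding. The consequence is stated without qualification: "Patients whose treatment is unblinded in this manner will be excluded from the final data analysis". Three statements in the same section limit its reach:

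- Unblinding is expected to be rare: "In general, it should not be necessary for unblinding to occur".
- Disclosure is promised: "The numbers of patients unblinded, and the reasons for the decisions will be specifically reported".
- A thromboembolic event is not accepted as grounds for unblinding.

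The exclusion sentence follows one about a safety evaluation of the thromboembolic rate. Its phrase about the manner of unblinding most naturally refers to the physician's request, the only patient-level unblinding the section describes.

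On the comparator, the Dosing section says: "The control group will receive equal volumes of and rates of normal saline". Patient Safety Monitoring states: "There had not been adverse effects of tranexamic acid reported". It also lets the data safety monitor unblind the collected data, if deemed necessary, to determine "if the study group is experiencing adverse events at a significantly higher rate or with greater severity than the control group".

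The document defines no intention-to-treat set, no safety set and no sensitivity analysis that includes unblinded patients. Data Collection has the coordinator split the data by randomisation number, but that only groups the patients who are retained.

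**The concern.** The exclusion is decided by something that happens after randomisation, and that event can be caused by the treatment. A genuine reaction to TXA cannot occur in a patient given saline. Suspicion formed under blinding can arise in either arm, so the imbalance is unknown rather than certain.

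Once excluded, a patient's transfusion, blood-loss, thromboembolic and wound outcomes all leave the between-arm comparison. The thromboembolic carve-out does not prevent this: a patient unblinded for a suspected reaction who later has a thromboembolic event is still lost from an outcome that the section itself calls primary. At 25 per arm, one such event is 1/25 = 4 percentage points.

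The pilot is not expected to be definitive, but under Sample Size and Feasibility its results decide whether a fully powered study is needed, and its stated purpose includes testing the procedures.

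**Working it through.** **Inputs from the plan.** Pilot of 25 + 25; transfusion rate 58%; a 30% decrease; 106 per arm for the future study (all from Sample Size and Feasibility). Read as relative, the decrease gives 0.7 × 58% = 40.6%. The relative reading fits the plan's sample size: 106 per arm is recovered by a one-sided pooled test of 58% against 41% (40.6% rounded) at alpha 0.05 and power 0.80, whereas an absolute 30-point drop to 28% would need only 42 per arm, two-sided. Nothing below depends on how 106 was derived.

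**Assumptions.** The plan gives no unblinding rate. I take 40% (10/25) as the TXA rate, so the true difference is 58.0 − 40.0 = 18.0 points. I let the excluded patients' risk lie 20 points below or above their arm's rate.

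**Formula.** Observed rate = (p − f·q)/(1 − f), where p is the arm's true rate, f the share excluded and q the risk in the excluded. If q = p, the observed rate is p for any f.

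**Single-arm results, 25 per arm.**
- TXA, f = 1/25: q = 0.20 gives 0.392/0.96 = 40.8%; q = 0.60 gives 0.376/0.96 = 39.2%.
- TXA, f = 2/25: q = 0.20 gives 0.384/0.92 = 41.7%; q = 0.60 gives 0.352/0.92 = 38.3%.
- Control, f = 1/25: q = 0.38 gives 58.8%; q = 0.78 gives 57.2%.

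**Observed difference (true value 18.0 points).**

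| Excluded: TXA, control | Excluded at lower risk | Excluded at higher risk |
|---|---|---|
| 0, 0 | 18.0 | 18.0 |
| 1, 0 | 17.2 | 18.8 |
| 2, 0 | 16.3 | 19.7 |
| 2, 1 | 17.1 | 18.9 |
| 1, 1 | 18.0 | 18.0 |

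**Extreme bounds, 2 excluded, both on TXA.** None transfused: 10/23 = 43.5%. Both transfused: 8/23 = 34.8%.

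**Against sampling error.** SE = √(0.58 × 0.42/25 + 0.40 × 0.60/25) = 13.9 points; 95% half-width 1.96 × 13.9 = 27.3. The 2-exclusion shift is 1.74/13.9 = 0.13 SE.

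**At 106 per arm, similar excluded share.** With 8 TXA patients excluded (8/106 = 7.5%), the TXA rate becomes 41.6% or 38.4%, a shift of 1.63 points. SE = 6.75 points, so the shift is 1.63/6.75 = 0.24 SE. If 4 controls are also excluded with the same offset, the shift falls to about 0.85 points (0.13 SE); with 8 and 8 it is zero.

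**Effect on the error rate, extreme case.** Suppose there is no true effect (58% in both arms), and 8 of 106 TXA patients, all transfused, are excluded. The TXA rate becomes (61.48 − 8)/98 = 54.6%, 3.4 points below control. By normal approximation, a nominal two-sided 5% test then rejects about 7.8% of the time.

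**The case against.** The strongest reply concerns size. The only study planned here is a 50-patient pilot with no confirmatory test. Unblinding is expected to be rare, and a shift of 0.13 SE within a half-width of 27.3 points is unlikely to change the decision to expand. The 20-point offset is an assumption: nothing in the plan links a suspected reaction to transfusion risk. The 106-per-arm study lies under Future Investigation, and the plan does not say that this rule would carry over. These points stand. They limit how serious the matter is, but they do not make the exclusion sound.

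The plan's safeguards help less than they seem to. Reporting numbers and reasons discloses the loss without restoring the outcomes, and reporting by arm is not promised. The data safety monitor's comparison is conditional, is confined to events beyond those reasonably expected after trauma surgery, and is not the final analysis. The statement that no adverse effects had been reported sits beside an eligibility criterion that excludes colour-blind patients because colour vision is used to detect toxicity, so the plan does contemplate drug effects.

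There is also a fair objection to retaining these patients. On transfusion, "the decision to transfuse will be left up to the individual treating surgeon", and the plan concedes that estimated blood loss is partly subjective. Outcomes judged after unblinding may therefore be coloured by knowledge of treatment. An analysis without unblinded patients shows how far this matters, but it brings back the selection problem and removes neither bias. That is a reason to report both analyses, with the randomised comparison as the main one.

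**Conclusion.** The concern holds. The plan prescribes an exclusion after randomisation that can depend on the assigned treatment, and nothing in it restores the excluded patients. The shift is zero if nobody is unblinded, if the excluded have their arm's average risk, or, in the illustrations above, if exclusions are equal between arms. Otherwise its direction cannot be predicted. Under the assumed moderate case it is at most 1.7 points (0.13 SE) in the pilot, which is small. For a constant excluded share the bias does not shrink as enrolment grows while the standard error does, so the rule would matter more in a larger study: 0.24 SE at 106 per arm with exclusions on TXA only. It should be corrected now, because the pilot is where the procedures are tested, but it does not invalidate the pilot.

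**What to change.** Replace the exclusion sentence in the Unblinding section with:

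> All randomised patients, including any whose treatment is unblinded, are analysed for efficacy in the arm to which they were randomised. All patients who received any study treatment are included in the safety comparison, grouped by treatment received. Outcome collection continues after unblinding. An analysis without unblinded patients is a sensitivity analysis only.

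Keep the commitment to report the numbers of, and reasons for, unblinding, and report them by arm.

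The cost is a few sentences. Data Collection already promises the listed items for every patient, but the plan does not say whether follow-up continues after unblinding, so this has to be stated. The plan should also say how patients who are randomised but never operated on are handled, since they have no operative outcomes. The criteria for unblinding and the management of the patient are unaffected.
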